Specific aim #1: Define functional nausea (FN) as an entity subdivided by measures of arousal, anxiety and gastric motor function.

Hypothesis: Adolescents with chronic nausea form subgroups based on clinical, physiologic and psychological parameters: 1) FN: characterized by high anxiety and emotional arousal, autonomic imbalance/low vagal tone and absence of major foregut dysmotility, 2) gastroparesis, and 3) poor gastric compliance. We will separate FN from other groups by clinical questionnaires, autonomic tests (heart rate variability) and gastric motility tests (gastric emptying, accommodation tests).

Specific aim #2: Demonstrate that resting state functional brain connectivity is different in female adolescents with FN compared to gender and age-matched healthy controls.

Hypothesis: Adolescents with FN will have altered rsFC between brain regions associated with emotional arousal neurocircuits (amygdala) and the top-down regulation of these by the prefrontal cortex. There will be decreased resting state functional connectivity between the ventromedial prefrontal cortex (vmPFC) and amygdala in adolescents with FN compared to healthy controls.

Specific aim #3: Demonstrate that four weeks of auricular neurostimulation improves nausea while strengthening the vagal tone and the abnormal resting state brain connectivity in female adolescents with FN compared to baseline and to more resemble that of healthy controls.

Hypothesis: 3a) Compared to baseline (pre-stimulation), there will be reduction in nausea and concurrent symptoms in the active compared to sham neurostimulation group after 4 weeks of therapy. 3b) Active neurostimulation therapy will increase vagal tone compared to baseline and also increase the rsFC between the vmPFC and amygdala in female adolescents with FN.

C. BACKGROUND, SIGNIFICANCE, AND RATIONALE

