Aim 3. *Hypothesis 3a): Four weeks of active neurostimulation will reduce nausea and concurrent symptoms from baseline compared to sham therapy as measured by weekly Nausea Severity Scale total score (primary outcome) after 4 weeks of therapy. Secondary outcomes include daily nausea (BARF) scores, and weekly nausea profile scores, upper GI symptoms (PAGI-SYM), abdominal pain (API), anxiety (SUDS, PROMIS and VSI), quality of life (PROMIS), disability (FDI) and co-morbid symptoms (CSI).* Another secondary efficacy variable will be the change in Nausea Severity Scale score after the second 4 weeks of therapy in a subset of subjects. We will compare pre and post total nausea, GI symptoms, anxiety, disability, quality of life and co-morbid symptom scores using a two-sided paired *t*-test at a Bonferroni corrected alpha of 0.05. Power: with ~40 in each group initially, allowing for 12% dropout based on our prior study, we will have ~35 subjects and 80% power to detect a difference of at least XX standard deviations (SD). We will similarly compare the other variables. Further we will use regression and regression trees with final value as the outcome and demographics, baseline values and overall symptoms as covariates. *Hypothesis 3b: Adolescents with FN will have reduced vagal tone as measured by HRV. Active neurostimulation therapy will elevate vagal tone compared to baseline and sham therapy, resembling that of healthy controls.* We will similarly analyze the change in vagal tone in nausea subjects. Further we will compare

the final vagal tone to healthy using a two sample t-test of equivalence where equivalence will be defined as within 20%. See fMRI analysis section for details on resting state fMRI analyses.

Longitudinal Continuous Variables

The efficacy parameters of longitudinal continuous variables such as nausea and pain will be analyzed using a mixed effects covariance pattern model to utilize all the data collected over time with consideration of the variance-covariance matrix of the repeated measures. This method allows a general unstructured variance-covariance matrix and allows patients to have incomplete data across scheduled time points. The method applied is also known as mixed-effects repeated measures analyses (MMRM).

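### Hypothesis 3a is active versus sham, but its own paragraph tests pre versus post; the between-arm model is never assigned to it, the detectable difference is blank, and the significance rules conflict

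*Combined protocol and SAP*

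**What the plan says.** All references are to the combined protocol and SAP.

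- **Hypothesis.** Section B, Specific aim #3, expects "reduction in nausea and concurrent symptoms in the active compared to sham neurostimulation group after 4 weeks of therapy". Under Power, Aim 3, the outcome is fixed "as measured by weekly Nausea Severity Scale total score (primary outcome) after 4 weeks of therapy".
- **Test in the same paragraph.** "We will compare pre and post total nausea, GI symptoms, anxiety, disability, quality of life and co-morbid symptom scores using a two-sided paired" (a *t*-test is meant). Its significance level is then set "at a Bonferroni corrected alpha of 0.05". No number of comparisons is given. The text does not say whether the arms are tested separately or pooled.
- **Power.** Starting from about 40 per group with 12% dropout, "we will have ~35 subjects and 80% power to detect a difference of at least XX standard deviations (SD". No test is named, and it is not said whether the SD is that of the score or of its change. Missing Data Handling says that the calculation was done in PASS 13.
- **Mixed model.** Under Longitudinal Continuous Variables, "The efficacy parameters of longitudinal continuous variables such as nausea and pain will be analyzed using a mixed effects covariance pattern model". The model has treatment, visit and treatment-by-visit terms plus baseline terms, is labelled primary, and runs to the end of the study.
- **Later text.** Continuous/ Ordinal variables gives a Mann-Whitney comparison of the two groups as the fallback. Additional Analysis then refers back to a primary analysis already described, without naming it.
- **Significance elsewhere.** Additional Analysis, and again the NDT subsection, present unadjusted p-values for every efficacy variable. Section O sets the cut-off at p < .05.

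**The concern.** A paired pre/post test asks whether scores moved. Hypothesis 3a asks whether they moved more under active stimulation than under sham. Change common to both arms (natural course, regression to the mean, response to wearing a device) counts as effect in the first and cancels in the second. If the paragraph is followed as written, 3a could be declared supported when the device does nothing.

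The mixed model would not do this, but the plan does not say which of the two analyses decides 3a. With XX unfilled and no test named, the reader also cannot tell what active-versus-sham difference the sample was meant to find. The significance rules differ enough that one p-value can be positive under one section and negative under another. The Bonferroni sentence lists total nausea first, so the primary outcome itself appears to sit inside the corrected family.

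**Working it through.** **1. The plan's own figure.** 40 × (1 − 0.12) = 35.2, so the stated 35 reproduces as a per-group number (both groups together would be 80 × 0.88 = 70.4). The treatment protocol section allows 40-50 per arm; the upper end gives 50 × 0.88 = 44. The detectable difference cannot be reproduced because no value is printed.

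**2. Candidate values for XX** (80% power, two-sided 0.05, noncentral *t*). The normal approximations are:

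- two-sample: d = (1.960 + 0.842) × √(2/n)
- paired: d = (1.960 + 0.842) / √n

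| Test | n | Normal approx. | Noncentral *t* | Unit |
|---|---|---|---|---|
| Active v sham, two-sample | 35 per arm | 0.670 | 0.679 | SD of the variable compared |
| Active v sham, two-sample | 44 per arm | 0.597 | 0.604 | SD of the variable compared |
| Pre v post, paired | 35 | 0.474 | 0.487 | SD of within-patient change |

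Suppose XX had been taken from the paired test. A two-sample test on change scores at 0.487 SD of change has noncentrality 0.487 × √(35/2) = 2.04 against a critical value of 1.995 (68 df), which is 52% power rather than 80%.

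**3. The paired test with no device effect.** For one arm of 35 the noncentrality is δ × √35, where δ is the change common to both arms in SD of change, and the critical value is 2.032 (34 df). The documents give no value for δ, so a range is shown.

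| Assumed δ | Noncentrality | Chance that the paired test is significant |
|---|---|---|
| 0 | 0 | 5% |
| 0.2 | 1.18 | 21% |
| 0.3 | 1.77 | 41% |
| 0.5 | 2.96 | 82% |

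The active-minus-sham contrast stays at 5% in every row.

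**4. Significance rules side by side.**

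| Place | Rule |
|---|---|
| Power, Aim 3 | Bonferroni, no divisor, family starting with total nausea |
| Additional Analysis; NDT | No adjustment for any efficacy variable |
| Section O | p < .05 |

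Two divisors serve as illustrations only, since the documents state none.

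- *Six*, for the score domains in the Bonferroni sentence: 0.05/6 = 0.0083. A p-value between 0.0083 and 0.05 changes verdict by section. If the primary is inside that family, its between-arm detectable difference with 35 per arm rises from 0.68 to 0.85 SD.
- *Eleven*, for the secondaries named in Aim 3 (ten scores plus the Nausea Severity Scale change after the second 4 weeks): 0.05/11 = 0.0045. The detectable difference is 0.91 SD, and power at 0.68 SD falls from 80% to 47%. With no adjustment, the chance of at least one false positive in 11 independent tests is 1 − 0.95^11 = 43%.

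**The case against.** The best defence is that the plan already has a between-arm primary. The mixed model covers efficacy variables of which nausea is a named example, and the primary outcome is a weekly nausea score. The model carries treatment terms and the label primary, and the Mann-Whitney fallback is between groups. The later reference to a primary analysis follows this text. On the time point, EAD placement details equates the end of the study with post-neurostimulation #1. The paired test may have its own role too, since Aim 3 also speaks of change from baseline.

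Most of this stands. A reader might infer that the plan contains no active-versus-sham analysis of nausea; the documents do not support that. What remains is narrower. Nausea covers at least three instruments here (Nausea Severity Scale, BARF, Nausea Profile), and no sentence gives the model 3a, the primary scale or a Post #1 contrast. Protocol and Procedures adds a further 4 weeks of active therapy, so the model's end point should be written out. The paired test is nowhere called descriptive. The regression and trees added in the same paragraph list demographics, baseline values and overall symptoms as covariates, not treatment.

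On multiplicity, unadjusted p-values could be printed and still judged against a corrected alpha. That would reconcile two of the rules, but Section O sets the cut-off at .05 and no divisor exists to apply.

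A reader might also infer that XX came from the paired test and that the trial is underpowered. The documents do not show which test was entered in PASS 13, so this is only a possibility to check.

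**Conclusion.** The point holds as a failure to fix in advance which analysis decides the primary hypothesis, together with a missing detectable difference and contradictory significance rules. It does not hold as a claim that a between-arm analysis is absent.

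The false-support figures of 21%, 41% and 82% describe the paired test in one arm of 35 under assumed common changes of 0.2, 0.3 and 0.5 SD; they are not a forecast for this trial. The detectable differences of 0.68 and 0.60 SD rest on the plan's own dropout rate and arm sizes, 80% power and an unadjusted two-sample test at two-sided 0.05. They do not depend on an assumed correlation. The figures for divisors of 6 and 11 show how far verdicts could move and are not measured error rates. The alpha conflict should not be read as touching the secondaries alone, because the Bonferroni family as written appears to include the primary.

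This should be corrected before unblinding.

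**What to change.** 1. **Decide 3a.** State that it is decided by the mixed-model active-minus-sham difference in Nausea Severity Scale total at Post #1, two-sided alpha 0.05, using randomised-phase visits only. Label the paired pre/post tests as descriptive within-arm change.
2. **Fill XX.** Give a between-arm figure with its test and SD unit. An unadjusted two-sample *t*-test at 80% power gives 0.68 SD of the variable compared with 35 per arm, or 0.60 with 44. If the PASS 13 run was for the paired test (0.49 SD of change), recompute it.
3. **Keep one multiplicity rule.** Take the single primary out of the Bonferroni family and test it at 0.05. For the secondaries, use either Holm or Bonferroni with a stated divisor, or an explicit label of nominal and exploratory. Delete the conflicting sentences in Power (Aim 3), Additional Analysis and NDT, and align Section O.

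The cost is wording only, with no new data or visits. The downside is a less favourable detectable difference than a paired-test figure would show, and lower power for each secondary if those are corrected.

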- Patients must have an intact external ear that is free of infection or severe dermatological conditions, have stable vital signs for their respective age, no history of seizures and no currently implanted electrical device
- Subjects included in the FN group include those who meet Rome IV criteria for functional nausea and have:
 - 1) autonomic imbalance with low vagal tone defined as baseline resting supine RMSSD value 2 or more standard deviations below the mean on HRV measurements, and
 - 2) normal gastric motor function (absence of gastroparesis or impaired accommodation). The gastric motor function and HRV tests will be compared to normative values obtained through a separate, ongoing, IRB-approved protocol (# 1030543-2)

Exclusion Criteria (Nausea and IBS Groups):

- Other pain-related diseases or somatization disorder
- Mental retardation or pervasive developmental disorder or epilepsy
- Psychosis
- Genetic or chromosomal disorders
- Pregnancy
- Subjects who admit to substance abuse during screening
- Patients with findings of peptic ulcer disease, H.pylori gastritis, celiac disease, inflammatory bowel disease, allergic disorders, or any chronic condition or medication that may cause nausea or pain
- Patients who are treated with opioids or who had any changes in their medical regimen in the past four weeks prior to study
- Patients with a history of allergy to adhesives
- Patients with a lactose intolerance

Study Design Overview

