Prior to any study procedures, subjects will be carefully screened for any allergies to Spirulina, egg, milk, or wheat allergens, lactose intolerance as well as use of medications. Subjects will be instructed that some discomfort may be expected during the nutrient drink test. They will also be notified that they may experience symptoms of nausea, fullness, bloating or pain. However, since the test is designed to cease when maximum satiety is reached, we do not expect significant symptoms to occur.

Heart Rate Variability

HRV reflects the variability of the R-R interval in the electrocardiogram and its frequency domains.⁸⁴ HRV is an indirect measure of central autonomic control and an indicator of overall psychological well-being.⁸⁵ Reductions in resting HRV reflect decreases in vagal output. The high frequency range of HRV is considered representative of vagal (parasympathetic) activity and studies show altered vagal tone as measured by HRV in subjects experiencing nausea.⁸⁶ All subjects will undergo a 9 minute baseline HRV measurement (3 minutes sitting, 3 minutes standing and 3 minutes sitting) after 10 minutes of rest. This will be repeated 20 minutes into neurostimulation and following the end of therapy. Data will be compared to the healthy controls from IRB protocol (#1030543-5). Recordings will be performed supine, sitting and standing to assess baroreflex response. HRV indices such as Respiratory Sinus Arrhythmia (RSA), low frequency domains, low/high frequency ratio and the time domain RMSSD as a surrogate of vagal tone⁸⁴ will be analyzed using CardioEdit/Batch software. The RSA values will be the primary HRV outcome and compared to baseline pre-neurostimulation and previously collected normative data from age-matched, healthy controls.

Questionnaires:

All patients will complete the questionnaires listed below. Patients are allowed to skip any questions that they do not feel comfortable answering. A member of the research team will introduce each questionnaire and explain the instructions to each of them.

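### The premise of Hypothesis 3b, that FN patients have reduced vagal tone, cannot be tested in an FN group selected for low RMSSD

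*Combined protocol and SAP*

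**What the plan says.** Section D, Inclusion Criteria (Nausea and IBS Groups), defines the FN group: "Subjects included in the FN group include those who meet Rome IV criteria for functional nausea and have" two further features. One is normal gastric motor function. The other is "autonomic imbalance with low vagal tone defined as baseline resting supine RMSSD value 2 or more standard deviations below the mean on HRV measurements". The reference is external: "The gastric motor function and HRV tests will be compared to normative values obtained through a separate, ongoing, IRB-approved protocol (# 1030543-2".

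The Heart Rate Variability section lists several HRV indices, among them "the time domain RMSSD as a surrogate of vagal tone". It names RSA as the primary HRV outcome, to be compared with the pre-stimulation value and with age-matched normative data. The source is again the separate protocol, cited with a different suffix: "Data will be compared to the healthy controls from IRB protocol (#1030543-5".

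The Power section, under Aim 3, states as the first sentence of Hypothesis 3b: "Adolescents with FN will have reduced vagal tone as measured by HRV". The rest of 3b concerns the rise in vagal tone under active stimulation. Specific aim #1 in Section B uses the same feature in describing the subgroup: "FN: characterized by high anxiety and emotional arousal, autonomic imbalance/low vagal tone and absence of major foregut dysmotility".

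**The concern.** A group cannot supply evidence for the feature by which it was chosen. If low vagal tone is an entry condition for FN, finding low vagal tone in FN shows that the entry condition was applied. It does not show that functional nausea goes with low vagal tone.

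This matters because the Background builds its disease model on autonomic dysregulation and reduced vagal tone in FN. A report that FN patients had markedly lower HRV than healthy adolescents would read as support for that model while carrying almost no information about it. No section says that the opening sentence of 3b will be examined in nausea patients before the RMSSD criterion is applied.

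**Working it through.** **Figure in the plan.** There is none to reproduce. The documents give no sample size, effect size or power for this premise, and no HRV means, SDs or correlations.

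**Inputs.**
- From the inclusion criteria: RMSSD cut at −2 SD.
- From the Heart Rate Variability section: RSA is the primary HRV outcome.
- From Study Population: 80-100 nausea patients.
- Assumed: HRV indices normal on a suitable scale, expressed in healthy-control SD units; RMSSD-RSA correlation r between 0.3 and 0.9.

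**Step 1: RMSSD with no disease effect.** Let Z be standard normal in patients and controls alike. The mean of those selected is

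E[Z | Z < −2] = −φ(2)/Φ(−2) = −0.0540/0.02275 = −2.37.

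Without any distributional assumption, the FN mean must still be −2 SD or lower, because every member is.

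**Step 2: the FN mean hardly responds to the truth.** Shift the whole nausea population by m SD and apply the same cut:

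| True shift m | Share below cut | Mean RMSSD of those selected |
|---|---|---|
| 0 | 2.3% | −2.37 |
| −0.5 | 6.7% | −2.44 |
| −1.0 | 15.9% | −2.53 |

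A true shift of a full SD moves the FN mean by only 0.16 SD (2.53 − 2.37) but raises the share below the cut about sevenfold (15.9/2.3). The information lies in how many patients qualify and in the unselected distribution, not in the mean of those who qualify.

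**Step 3: RSA with no disease effect.** Under a bivariate normal model the expected RSA in the selected group is r × (−2.37). Rejection rates are for a two-sided 5% t-test against healthy controls, from 4,000 simulated trials per case. The sizes are illustrative: 15 is the planned fMRI subset and 35 the expected completers per arm; the number of normative controls is not given.

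| r (assumed) | Expected RSA, SD | Rejects, 15 v 15 | Rejects, 35 v 35 |
|---|---|---|---|
| 0.9 | −2.14 | 100% | 100% |
| 0.7 | −1.66 | 99.9% | 100% |
| 0.5 | −1.19 | 91% | 99.98% |
| 0.3 | −0.71 | 47% | 85% |

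The nominal rate is 5%. Using RSA instead of RMSSD reduces the bias but does not remove it unless r is near zero.

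**Step 4: how many would qualify with no disease effect.** 80 × 0.02275 = 1.8 and 100 × 0.02275 = 2.3, so about 2 patients, before the motor-function requirement. Reaching 15 would take about 15/0.02275 ≈ 660 patients.

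**The case against.** The strongest reply is that the plan writes no baseline test of FN against healthy controls. Under Aim 3 it specifies the change in vagal tone among nausea subjects and an equivalence comparison of final vagal tone with healthy. The HRV section compares RSA with norms but does not confine that comparison to the RMSSD-selected group, so the investigators may have all nausea patients in mind. This stands as far as it goes: the fault is a hypothesis stated without a valid test, not a specified invalid test. It does not remove the problem, because the sentence names FN, the criteria define FN by the result, and the wording about nausea subjects concerns change under treatment.

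A second reply is that RSA, not RMSSD, is the primary HRV outcome. That stands against calling the RSA result a tautology, and the size of the RSA bias rests on an assumed correlation.

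A third reply is that a complete absence of disease effect would expose itself. With about 2 qualifying patients, the FN group could not be filled, and a filled group would itself point to an excess of low RMSSD. This also stands. A reader might infer that the trial would announce autonomic imbalance even if nausea were unrelated to vagal tone; at the enrolment planned, the group sizes simulated in Step 3 would not arise in that case. The rejection rates show the size of the bias, not a forecast of this trial.

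Finally, a reader might take Aim 1 to be circular as well. Aim 1 sets out to define and separate subgroups, and the Power section plans only to summarise their characteristics, so it is already descriptive.

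**Conclusion.** The point holds for one sentence. The premise that opens Hypothesis 3b cannot be tested in the FN group as the inclusion criteria define it. For RMSSD this follows from the definition alone; the figure of −2.37 SD needs normality. For RSA the comparison is biased towards low vagal tone by about 0.7 to 2.1 SD over the assumed correlations, and the documents do not allow a narrower range.

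A reader might infer that the trial's mechanistic question as a whole is circular. The documents do not support that. The active-versus-sham contrast in vagal tone is randomised, the connectivity hypotheses do not use RMSSD as their outcome, and the primary outcome is the Nausea Severity Scale; none of these is true by construction. The change should be made, but it concerns interpretation of a secondary mechanistic premise, not the main efficacy result.

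**What to change.** In the SAP:

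1. State that reduced baseline vagal tone will be tested in all enrolled patients with Rome IV functional nausea and normal gastric motor function, before the RMSSD criterion is applied, against the age-matched healthy controls of the separate normative protocol. Use RSA as the main measure and RMSSD as supportive.
2. Report the proportion of these patients below the RMSSD cut beside the proportion of healthy controls below the same cut. The control proportion is the proper benchmark; 2.3% is expected only if RMSSD is normally distributed.
3. Label baseline vagal tone in the RMSSD-selected FN group as descriptive of a selection criterion, not as confirmation of Hypothesis 3b.

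The cost is SAP wording only. Table 1 already schedules HRV at the pre-treatment assessment, the gastric tests are at Visits 1 and 2, and the plan already relies on the normative data. No patient, visit or test is added. Because the normative study is described as ongoing, the SAP should state which data cut from it supplies both the threshold and the comparison.

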Medical and psychological history will be obtained to verify eligibility and screen patients for alcohol, nicotine, and drug abuse following the completion of consent/assent documents. All eligible subjects will complete the questionnaires related to demographic, medical, and psychological factors including nausea, abdominal pain, IBS symptoms (Rome IV), anxiety, disability and quality of life (Table 1). This will take about 30 minutes total to complete. Subjects will then undergo baseline heart rate variability (HRV) measurements in clinic. Children will perform a self-assessment of the Tanner stage of pubertal development using a validated self-assessment form.

Visit 1: Subjects will undergo the ¹³C gastric emptying breath test (GEBT) (Table 1). See section on ¹³C GEBT for details and attached protocol.

Visit 2: Subjects will undergo Satiety Drink Test (see SDT section and attached protocol).

Visits 3-6: Subjects will complete questionnaires as per Table 1 followed by neurostimulator placement by study physician. These visits will be repeated weekly and take about 20-40 minutes to complete. HRV will be measured before and after the EAD placement at Visit 3 and 6.

Post-neurostimulation #1: Subjects will not return but will complete questionnaires (Table 1) at the end of 4 weeks of therapy which will be mailed back to the research team. Participants in fMRI sub-study will undergo repeat fMRI scan (post-scan) at this visit and complete questionnaires per Table 1.

Post-neurostimulation #2: All subjects will return to clinic for their regularly scheduled clinic follow-up visit 2 months after end of therapy and will complete questionnaires as per Table 1.

Subsequent to the initial 4 weeks of therapy, subjects will undergo another 4 weeks of **active neurostimulation therapy (visits 7-10) with the exact same protocol as during the first round of treatment. A post-neurostimulation #3 questionnaire assessment will be completed (just as with post-neurostimulation #1) although no repeat fMRI scans will be performed at this time. Similarly, a post-neurostimulation #4 clinic visit will be scheduled 2 months after the end of the second 4 week of therapy.

Optional fMRI Sub-study

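### Hypothesis 3b is a sham-controlled claim about vagal tone, but the only test indicated for it is a within-group paired t-test, which regression to the mean can bias in subjects selected for low HRV

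*Combined protocol and SAP*

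**What the plan says.** **Hypothesis.** Specific aim #3 (Section B) states 3b against baseline only: "Active neurostimulation therapy will increase vagal tone compared to baseline". The analysis section (Section F, Statistical Analysis, Power, Aim 3) adds the control arm: "Active neurostimulation therapy will elevate vagal tone compared to baseline and sham therapy, resembling that of healthy controls".

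**Test.** The same paragraph then says "We will similarly analyze the change in vagal tone in nausea subjects". The test it has just set out for pre and post scores is a two-sided paired t-test at a Bonferroni-corrected 0.05. A two-sample equivalence test of final vagal tone against healthy subjects, with a 20% margin, follows. The repeated-measures model under Longitudinal Continuous Variables has a treatment term and a baseline covariate, but gives nausea and pain as its examples and does not name HRV.

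**Selection.** The FN group (Section D, Inclusion Criteria) requires "autonomic imbalance with low vagal tone defined as baseline resting supine RMSSD value 2 or more standard deviations below the mean on HRV measurements".

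**Readings.** Under Pre (Baseline) in Section D: "Subjects will then undergo baseline heart rate variability (HRV) measurements in clinic". In the same section: "HRV will be measured before and after the EAD placement at Visit 3 and 6". The Heart Rate Variability section names the outcome: "The RSA values will be the primary HRV outcome and compared to baseline pre-neurostimulation and previously collected normative data from age-matched, healthy controls". The plan does not say which reading is the analysis baseline for change in vagal tone.

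**The concern.** A subject chosen because one reading was extremely low will on average read higher next time, treated or not. A paired test from that same reading cannot separate this drift from a device effect. Both statements of 3b concern FN, the group defined by the low reading. A rise within the active arm could therefore be reported as the device strengthening vagal tone, which is the mechanistic claim of Aim 3.

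The same drift carries final values towards the healthy norm, which favours the equivalence claim. The sham arm does not protect that comparison, because its reference group is external.

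Apart from any bias, a within-group test does not answer a hypothesis stated against sham.

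**Working it through.** **Inputs from the documents:** selection at or below −2 SD on supine RMSSD; RSA as primary HRV outcome; 1:1 randomisation of 80–100 nausea subjects; about 40 per group with 12% dropout; HRV at Pre and before and after placement at Visits 3 and 6.

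**Assumed, not in the documents:** patients' RMSSD is normal with SD 1 in normative units and mean m = 0 or −1; retest correlation ρ = 0.5–0.9 (0.6–0.9 in the simulations); RSA–RMSSD correlation q = 0.8–1.0; 10 to 35 FN subjects per arm.

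**1. The plan's own figure.** 40 × (1 − 0.12) = 35.2, which agrees with the stated ~35. No detectable difference is given, so there is none to reproduce. At 80% power and two-sided 0.05, the noncentral t gives 0.49 SD for a paired test with 35 and 0.68 SD for a two-sample test with 35 per arm.

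**2. Which reading selects.** FN subjects in the fMRI sub-study are scanned after subgrouping and before the first placement, at Visit 3. Classification therefore comes before Visit 3, and the only earlier HRV in Table 1 is at Pre. This is an inference from the schedule; the plan does not state it.

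**3. Expected untreated rise.** With c = −2 − m, selected subjects lie on average λ = φ(c)/Φ(c) below their population mean, and the expected rise on retest is (1 − ρ)λ.
- m = 0: λ = 0.0540/0.0228 = 2.37
- m = −1: λ = 0.2420/0.1587 = 1.53

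| ρ | 0.5 | 0.6 | 0.7 | 0.8 | 0.9 |
|---|---|---|---|---|---|
| Rise, m = 0 (SD) | 1.19 | 0.95 | 0.71 | 0.47 | 0.24 |
| Rise, m = −1 (SD) | 0.76 | 0.61 | 0.46 | 0.31 | 0.15 |

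For RSA, multiply by q: at m = 0, ρ = 0.7, q = 0.8, the rise is 0.8 × 0.71 = 0.57 SD.

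**4. False-positive rates with no device effect** (simulation, 2,500 trials per setting, two-sided 0.05, ρ = 0.6–0.9, q = 0.8–1.0):

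| Analysis | n = 10 | n = 35 |
|---|---|---|
| Paired, selecting reading as baseline, m = 0 | 23–90% | 70–100% |
| Paired, selecting reading as baseline, m = −1 | 13–55% | 35–99% |
| Active v sham change, HRV-selected | 4–6% | 4–6% |
| Paired, Visit 3 pre-placement baseline | 4–6% | 4–6% |

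With no HRV selection (all nausea subjects, n = 35, ρ = 0.7) the paired test gives about 5%.

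**5. Effect of alpha and q.** At n = 15, m = −1, ρ = 0.7–0.9, the paired test gives about 24–63% with q = 1 and 17–42% with q = 0.8. With q = 0.8 and an assumed eight-test Bonferroni level it gives 4–14%, against a nominal 0.05/8 = 0.6%.

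**6. Whether n and m fit together.** At m = −1 the fraction selected is 0.159, so 80–100 subjects would yield 80 × 0.159 = 13 to 100 × 0.159 = 16 meeting the RMSSD criterion, or about 6–8 per arm. At m = 0, 100 × 0.0228 = 2. An FN arm of 35 would need a much lower centre, and the rise would then be smaller: at m = −2, λ = 0.399/0.5 = 0.80, giving 0.08–0.40 SD. The n = 35 column is therefore the top of the range. The n = 10, m = −1 cell is closer to what the planned enrolment would supply.

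**7. Equivalence.** Mean position at selection is −2.37 (m = 0) or −1 − 1.53 = −2.53 (m = −1). Adding the rise gives −2.13 to −1.18, or −2.38 to −1.77. The drift is towards the norm but leaves selected subjects more than 1 SD below it. The documents give no normative mean and SD, so the 20% margin cannot be put on this scale.

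**The case against.** A reader might infer that regression to the mean will be mistaken for a device effect in this trial. The documents do not support that certainty, for five reasons.

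- **Sham.** The analysis section states 3b against sham as well as baseline, and the trial is randomised 1:1. Expected drift is equal in the two arms and cancels in an active-versus-sham comparison. The list of variables for the repeated-measures model is illustrative and does not exclude HRV. This stands; what is missing is a statement that a between-arm test decides 3b for HRV.
- **Baseline.** The Visit 3 pre-placement reading is a second pre-treatment value, and the pre-neurostimulation baseline of the Heart Rate Variability section may well mean that one. If so, the problem largely disappears. This stands as a possibility; the plan does not settle it.
- **Population.** The analysis sentence refers to nausea subjects, and all 80–100 are randomised. Without the RMSSD cut-off, this selection effect is absent. Against that, both versions of 3b are about FN.
- **Variable.** Selection is on RMSSD and the outcome is RSA. This shrinks the artefact in proportion to their correlation but does not remove it unless they are unrelated.
- **Size.** Reliability, correlation, the patients' mean and the FN sample size are all assumed, and a Bonferroni level lowers the rates. This stands, and no single false-positive rate should be quoted as the trial's own.

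Nor does the drift by itself establish equivalence to healthy subjects; it only moves the result in that direction.

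**Conclusion.** The point holds as a gap between hypothesis and test, with a conditional bias attached. The plan names no between-arm test for vagal tone, and the test it points to does not address the sham comparison in its own hypothesis.

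If the selecting reading is also the baseline and FN subjects are analysed, an untreated RMSSD rise of 0.24–1.19 SD (patients centred on the norm) or 0.15–0.76 SD (centred 1 SD below) is expected for reliability 0.5–0.9. The paired test then exceeds its nominal level throughout the settings examined, by an amount that the documents cannot fix. If any one of the three conditions fails (selecting reading as baseline, FN-only population, within-arm test), the false-positive rate for change is about 5%. This concerns a secondary, mechanistic outcome; the primary outcome, the Nausea Severity Scale, is not affected.

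**What to change.** In the Aim 3 analysis text:

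1. Name active versus sham on RSA as the test of Hypothesis 3b, by ANCOVA or the repeated-measures model already in the plan, adjusted for the Visit 3 pre-placement reading.
2. State that the Pre-visit HRV is used for classification only.
3. State whether the population is FN or all randomised nausea subjects.
4. Name the outcome reading. The Heart Rate Variability section promises one after the end of therapy, while Table 1 schedules none after Visit 6.
5. Report within-arm change as descriptive and the comparison with healthy norms as supportive. Align the wording of 3b in Section B with that in Section F.

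The cost is SAP wording, since the Visit 3 and Visit 6 readings are already scheduled. The downside is lower nominal power: 0.68 SD detectable with 35 per arm, against 0.49 SD for the paired test (the former before any gain from baseline adjustment), and larger still if only FN subjects are analysed.
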